Online Data Collection Evaluating UCSF Sales Ban: Observational data from an online survey of 2556 UCSF employees suggests that higher-risk demographic groups could disproportionately respond to the proposed intervention. Sample retention in this online study was 89% at the 12-month follow-up. Ethnic minority employees were twice more likely to report heavy consumption at baseline. Latinos experienced a more pronounced decline following the sales ban than Whites (by -3.7oz/day, $p < .007$). The lowest occupation stratum (service/manual workers) experienced a 30% reduction in consumption compared to 13% in the highest occupational group (academic medicine faculty) ($p < .0001$). *While limited by an observational approach, this study supports our proposed analyses by ethnic minority and lower occupational status, and speaks to our capacity for online data collection with good retention.*

Pilot Study of SSB Craving as a Mechanism: A published analysis of the UCSF pilot data found variable responses to the interventions for those with stronger SSB cravings (+1 SD above sample mean at baseline).¹² Individuals with weaker (-1 SD) SSB cravings reduced their SSB consumption, on average, by 12.8 oz/day ($p = .02$) more than individuals with stronger SSB cravings. However, among those with stronger cravings, those randomized to the multilevel intervention had significantly greater reductions in daily consumption (-19.21 oz/day vs. -2.49 oz/day, $p < .001$), a difference of 16.72 oz/day. *This study informs analyses proposed under Aim 3 by suggesting that employees with stronger SSB cravings may need the added motivational boost of brief counseling to achieve benefits on a par with others.*

Current Controlled Trial of Workplace Sales Ban in Sutter Health: In partnership with Sutter Health, we are currently completing a fully powered controlled trial of workplace SSB sales bans across 8 hospital campuses (5 intervention sites and 3 controls, $N = 657$ employees), funded by the [name] and John Arnold Foundation. Retention was 88% at 6 months and 78% at 12 (during the COVID-19 pandemic). Collection of anthropometrics for this controlled trial was interrupted by the pandemic, but we continue to collect dietary assessments and other data using an online format. At 6-months post-sales ban, there is a

**SUTTER HEALTH
INSTITUTIONAL REVIEW BOARD**

Protocol Summary Form

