Analysis Plan for Aim 3: (Exploratory): *How does the intervention work?* We will test whether changes in SSB craving mediate the effects of the multilevel intervention on outcomes.

Introduction: The goal of this analysis is to examine SSB craving as a mediator in the relationship between the multilevel intervention and primary and secondary health outcomes. This is justified by our pilot study analysis showing that employees with a high level of baseline craving benefited more from the multilevel intervention than comparable employees exposed to the sales ban alone.¹² This study is designed to test the mediation model for the sales ban and brief intervention separately, helping us to understand the “active ingredients” in the multilevel intervention. We can also explore differential benefits for members of high-risk groups.

Research Design for Aim 3: This exploratory analysis will estimate mixed effects using logistic regression models. In contrast to some approaches toward mediation analysis (e.g.,¹¹¹⁻¹¹⁴), ours will

**SUTTER HEALTH
INSTITUTIONAL REVIEW BOARD**

Protocol Summary Form

simultaneously test all paths, including indirect effects through the mediator,¹¹²⁻¹¹⁴ regardless of the presence of a statistically significant total intervention effect.¹¹⁴ Available measures allow us to examine the extent that changes in SSB cravings and SSB consumption after cravings mediate the effects of the multilevel intervention on outcomes.

Key Measures for Aim 3: In addition to measures described above, this aim incorporates text message-based EMA data that captures SSB cravings in the context of day-to-day life.

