Analytic Plan for Aim 3: Participants will respond to a question asking if they experienced a craving for SSBs as *yes* or *no*. We will use this SSB craving variable (M), along with group assignment (X), to predict 12-month SSB consumption (Y). This simultaneous mediation model will comprise, first, a mixed effects logistic regression model (Path A in Figure 2 above, from X to M). This model will include random effects for day nested within study period, nested within person for each of the possible reports per day (morning, afternoon, evening, and “any other time not previously reported”). The dependent variable will be the dichotomous primary outcomes reflecting the experience of a craving or whether a craving was acted upon. Model covariates (fixed effects) include time of day, study period, randomization group, and the interaction of study period by randomization group. This will allow us to estimate the odds of having a craving or indulging in one at 6- and 12-months compared to baseline, separately for each experimental arm, as well as allowing for direct comparisons between study arms at each time point.

A second component of the model is a mixed effects linear regression model (Path B in Figure 2 above, from M to Y) that links a change in cravings between baseline and the 6-month follow up (measured as the change in the proportion of responses in which subjects reported cravings) to SSB consumption and HOMA at 12 months. We will perform this mediation model first without covariates¹¹⁵ and then will perform it with other predictors of SSB consumption (e.g., demographics, high-risk group) as in Aim 1. This analysis will allow us to estimate the proportions of variance in SSB consumption at 12 months that are related to changes in SSB craving experiences.

The relationship between the interventions and SSB consumption without the inclusion of craving (Path C) will have already been established in the analyses for Aims 1 and 2, so lastly, we will examine Path C' (interventions predicting consumption and waist change with the inclusion of the craving mediator). This will necessitate a model similar to those used in Aims 1 and 2, but with the addition of craving change and an interaction term for intervention*craving change.

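### Paths B and C' enter craving only as a baseline-to-6-month change, without baseline craving, so the slope in general does not estimate the effect of 6-month craving on the 12-month outcome

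*Combined protocol and SAP*

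**What the plan says.** Section (4c), Analytic Plan for Aim 3, first states what goes into the mediation model: "We will use this SSB craving variable (M), along with group assignment (X), to predict 12-month SSB consumption (Y"). Path B is then a mixed linear model that "links a change in cravings between baseline and the 6-month follow up (measured as the change in the proportion of responses" with a craving) "to SSB consumption and HOMA at 12 months". The predictor is a change and the outcome is a later level.

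Two versions are planned. "We will perform this mediation model first without covariates", the plan says, and "then will perform it with other predictors of SSB consumption (e.g., demographics, high-risk group) as in Aim 1". The Aim 1 example for HOMA lists the two interventions, the baseline value of the outcome, baseline SSB intake, baseline BMI, race or ethnicity, and sex. The Aim 2 list adds the interaction of the two interventions and job classification. Neither list has baseline craving.

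Path C' is a model like those of Aims 1 and 2 with two craving terms added: craving change, and its interaction with intervention.

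**The concern.** A change score alone gives the two waves of craving equal and opposite coefficients. That is right only if the outcome really depends on the difference. If 12-month intake depends mainly on how much a person still craves at 6 months, the model is misspecified. Two people with the same 6-month craving then get different predictor values because they started at different levels, and the slope is diluted.

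Path B supplies the second leg of the indirect effect, so any distortion passes straight into the mediated effect. The Significance section says Aim 3 will help build more effective future interventions if this one does not work. A weak Path B slope could then be read as evidence against craving as the mechanism when it partly reflects the coding of the mediator.

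**Working it through.** The documents state no figure for Path B and no power calculation for Aim 3, so there is nothing to reproduce.

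**Inputs from the documents**
- Predictor: D = M6 - M0, the 6-month minus the baseline craving proportion.
- Outcome: the 12-month level, with group assignment in the model, so the craving slope is a within-arm slope.
- N at 12 months: 550 (Power Calculations).
- Craving reports: texts go out on four days per period, and the craving item is in the evening battery, so about four yes/no reports per period.

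**Assumed, because the documents give no value**
- b6 and b0; the within-arm SDs s6 and s0; the between-wave correlation rho; the correlation of baseline SSB intake with baseline craving.

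**Step 1. Slope without covariates.** Let `Y = b0·M0 + b6·M6 + e`. The slope on D alone is

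`[b6(s6² - rho·s0·s6) - b0(s0² - rho·s0·s6)] / (s0² + s6² - 2·rho·s0·s6)`

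- If b0 = -b6, numerator and denominator match and the slope is b6. This is the case in which only change matters.
- If s0 = s6, the slope is (b6 - b0)/2 for any rho. With b6 = 1 it is 0.50 at b0 = 0, 0.25 at b0 = 0.5, 0.00 at b0 = 1 and -0.25 at b0 = 1.5.
- If s6/s0 = 0.7, rho = 0.5 and b0 = 0: (0.49 - 0.35)/(1 + 0.49 - 0.70) = 0.14/0.79 = 0.18.
- If s6/s0 = 1.3, rho = 0.5 and b0 = 0: (1.69 - 0.65)/(1 + 1.69 - 1.30) = 1.04/1.39 = 0.75.

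**Step 2. Where the slope reaches zero.** This happens at `b0/b6 = (s6² - rho·s0·s6)/(s0² - rho·s0·s6)`. At equal SDs the ratio is 1. At rho = 0.5 it is 0.14/0.65 = 0.22 for an SD ratio of 0.7, and 1.04/0.35 = 2.97 for 1.3. So b0 must be about as large as b6 at equal SDs; the threshold is lower if the spread of craving narrows by 6 months and higher if it widens.

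**Step 3. Second planned model, with baseline SSB intake.** Assume unit SDs, rho = 0.5, intake correlated 0.5 with M0, and intake related to M6 only through M0 (correlation 0.25). Given intake:
- Var(M0) = 1 - 0.25 = 0.75
- Var(M6) = 1 - 0.0625 = 0.9375
- Cov(M0, M6) = 0.5 - 0.125 = 0.375
- Var(D) = 0.75 + 0.9375 - 0.75 = 0.9375

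Slope at b0 = 0: (0.9375 - 0.375)/0.9375 = 0.60 of b6. At b0 = b6: (0.5625 - 0.375)/0.9375 = 0.20 of b6.

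**Step 4. With baseline craving added.** Since M6 = M0 + D, `Y = (b0 + b6)·M0 + b6·D + e`. The slope on D is now b6 whatever b0, rho or the SDs are. Simulation with four arms gave 0.995 to 1.008 against a true value of 1, for b0 from -1 to 1.5 and rho from 0.3 to 0.7.

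**Step 5. What it means at N = 550.** Assume b6 = 0.2 SD, equal SDs, rho = 0.5 and craving measured without error. The simulated chance of a significant positive slope at b0 = 0 is 63% with the change score alone and 98% with baseline craving added. At b0 = 0.1 it is 20% against 98%.

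**Step 6. What remains after the fix.** In an assumed logistic-normal example with four yes/no reports per wave and a true slope of 10, the adjusted slope was 5.6 to 7.2. The change-only slope was -0.4 to 1.8.

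**The case against.** **The plan may be right as it stands.** Aim 3 asks whether changes in craving mediate the effect, and if only change matters the slope is unbiased. That stands, but as one special case. The model with baseline craving contains it, so nothing is lost by adding the term.

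**Path C' concerns change in the outcome, where a change score may be natural.** This does not rescue it. Path C' follows Aims 1 and 2, which adjust for the baseline outcome. `Y12 - Y0 = c + k·D + g·Y0` is the same model as `Y12 = c + k·D + (g + 1)·Y0`, so the craving coefficient k is unchanged.

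**The covariate list is open and Aim 3 is exploratory.** True. Baseline craving is not excluded, and baseline SSB intake in the second version reduces the bias. This limits the weight of the point; it does not settle what will be fitted.

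A reader might infer three stronger things that the documents do not support:
- *That Path B will show no mediation, or the wrong sign.* This depends on b0 and on the variances (step 2), none of which the documents give.
- *That the pilot shows b0 to be positive.* The Background reports: "Individuals with weaker (-1 SD) SSB cravings reduced their SSB consumption, on average, by 12.8 oz/day" more than those with stronger cravings. That is a marginal association with the reduction in intake, not an effect on the 12-month level at fixed 6-month craving. Take b6 = 20, b0 = 0, a between-wave correlation of 0.6, equal SDs and a baseline craving-to-intake slope of 10 (all assumed). Change in intake then has slope 20 × 0.6 - 10 = +2 on baseline craving. Stronger cravers reduce less although b0 is zero.
- *That a baseline-craving-by-intervention term is missing.* The Aim 3 introduction does rest on a finding of that kind: "employees with a high level of baseline craving benefited more from the multilevel intervention than comparable employees exposed to the sales ban alone". But moderation is a different question from mediation through change, so such a term is optional.

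**Conclusion.** The point holds as a specification gap in Paths B and C'. As listed, the models omit baseline craving. The craving slope then estimates the effect of 6-month craving only if baseline craving has an equal and opposite effect.

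With b0 = 0 and no covariates, the slope is half the true effect at equal variances, and 0.18 to 0.75 of it over the assumed SD ratios at a correlation of 0.5. In the covariate-adjusted version it is about 0.60 of b6 at b0 = 0 and 0.20 at b0 = b6, under assumed correlations of 0.5. The direction of the algebra is certain. The sizes rest on assumed variances and correlations, and no value of b0 can be taken from the documents. As Aim 3 is exploratory, this does not touch the primary analyses. It does affect whether a weak Path B result could be interpreted.

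**What to change.** In Paths B and C', add the baseline EMA craving proportion as a covariate. Entering the 6-month proportion adjusted for the baseline proportion is equivalent. Do this in both versions, so that the one without covariates means without covariates other than baseline craving.

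The cost is one model term, from text reports already collected at baseline.

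The plan should also say that the adjusted slope will still be attenuated by measurement error. The text-message section implies about four evening craving reports per period, whereas the Aim 3 analytic plan describes up to four reporting times a day. Stating which applies would let a reader judge that attenuation. An interaction of the baseline FCQ-T-r score with intervention may be added as a separate moderation analysis, but is not part of this correction.

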To assess the effectiveness of this multilevel intervention, called the workplace *Metabolic Health Improvement Program (MHIP)*, we will conduct a double-randomized trial in partnership with the clinical trials division of a large Northern California-based academic healthcare system, Sutter Health ($N=700$ employees on $N=16$ hospital campuses). We will first cluster-randomize 8 Sutter Health hospital campuses to the SSB sales ban condition and 8 campuses to serve as controls (no sales ban). Across these 16 campuses, we will further randomize heavy-SSB-consuming employees (>30 oz/week) to receive a brief SSB counseling intervention delivered remotely or to a control condition.^{11,12} The **primary outcomes** are central obesity (e.g., waist circumference) and change in serum insulin sensitivity (homeostatic model assessment [HOMA] ratio). **Secondary outcomes** include changes in SSB consumption, Body Mass Index (BMI), and lab values to include: lipid profile, triglycerides, triglyceride:HDL ratio, uric acid, ApoA, ApoB, lactate, ALT/AST, GGT, fasting glucose, fasting insulin, HbA1c. We will assess dietary composition remotely using the Automated Self-Administered 24-hour (ASA-24) at baseline, 6 and 12 months, and waist circumference remotely with empirically validated instructions and a standardized tape measure provided to participants. We will collect blood samples in the workplace labs at baseline and 12 months. All analyses will consider compensatory changes in at-home SSB intake, calories from sugar, and total calories. Aims are:

Aim 1: How well does each intervention work alone? We will assess the independent effects of the brief counseling intervention and workplace SSB sales ban on changes in primary and secondary outcomes. We will compare outcomes across employees exposed to the brief intervention only ($n=175$), SSB sales ban only ($n=175$), and no intervention ($n=175$). *We hypothesize that the brief counseling intervention and sales ban will each independently decrease waist circumference and HOMA relative to no intervention. Those at high risk (baseline BMI >25 , ethnic-minority, and lower-occupational status) will benefit more from the interventions.*

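### The exploratory Aim 3 mediation plan does not consistently define an indirect effect for HOMA or waist: the mediator changes between paths, and neither outcome is named in both Path B and Path C'.

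*Combined protocol and SAP*

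**What the plan says.** Section 1 names waist circumference and HOMA as the primary outcomes; SSB consumption is secondary. In section 4c, the introduction to the Aim 3 analysis plan sets the goal: to "examine SSB craving as a mediator in the relationship between the multilevel intervention and primary and secondary health outcomes". The Research Design for Aim 3 says the analysis will "simultaneously test all paths, including indirect effects through the mediator", and adds SSB consumption after a craving as a further candidate mediator.

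The Analytic Plan for Aim 3 then gives these pieces:

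- **Overall model.** "We will use this SSB craving variable (M), along with group assignment (X), to predict 12-month SSB consumption (Y").
- **Path A** (intervention to craving). A mixed-effects logistic model on individual reports: "The dependent variable will be the dichotomous primary outcomes reflecting the experience of a craving or whether a craving was acted upon". It compares 6 and 12 months with baseline, by arm.
- **Path B** (craving to outcome). A linear mixed model whose predictor is a person-level change from baseline to 6 months, "measured as the change in the proportion of responses in which subjects reported cravings". The outcomes are SSB consumption and HOMA at 12 months.
- **Path C** (total effect). Described here for SSB consumption and taken from Aims 1 and 2.
- **Path C'** (direct effect). "interventions predicting consumption and waist change with the inclusion of the craving mediator", using a model like those of Aims 1 and 2 plus craving change and its interaction with intervention.

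**The concern.** An indirect effect combines how far the intervention moves the mediator with how far the outcome moves per unit of that same mediator. Here Path A yields a log-odds for a single report, while Path B yields a slope per unit of a person's change in proportion. The time windows differ too, and acting on a craving has a Path A but no Path B. The two primary outcomes are split between Paths B and C'.

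The plan gives no formula, scale conversion or interval method to join the pieces. An analyst would either multiply coefficients that do not belong together, or choose the mediator, window and outcome form after seeing the data. Because the model includes an intervention-by-craving interaction, the mediated effect also depends on the intervention level at which it is evaluated, and none is stated. No other scheduled measure of SSB craving can stand in: the schedule of procedures in section 4b has the beverage craving questionnaire at baseline only.

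**Working it through.** The documents give no sample size, power or effect size for Aim 3, so there is no planned figure to reproduce. The check sets the paths side by side and then illustrates the consequence.

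**Step 1. Outcomes by path** (section 4c, Analytic Plans for Aims 2 and 3)

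| Outcome | Path B | Path C | Path C' |
|---|---|---|---|
| SSB consumption (secondary) | named | named | named |
| HOMA (primary) | named, 12-month value | via Aims 1 and 2, as change | not named |
| Waist (primary) | not named | via Aims 1 and 2 | named, as change |

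Path C exists for every outcome because the Aim 1 and 2 models are repeated for each primary and secondary outcome. Only SSB consumption is named in B, C and C'.

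**Step 2. Mediator by path**

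| | Path A | Paths B and C' |
|---|---|---|
| Unit | single report | person |
| Variable | craving yes/no, or craving acted upon | craving change (defined in Path B as change in proportion) |
| Scale | log-odds | proportion |
| Window | 6 and 12 months vs baseline | baseline to 6 months |

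Path A also lists morning, afternoon, evening and other reports. The section on text-based data collection has two texts a day on four days, with the craving item in the evening battery. That gives about 4 × 1 = 4 craving reports per person per period.

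**Step 3. Does the mismatch matter numerically?** All inputs here are assumptions, not figures from the documents: 550 people in two equal arms; 4 craving reports per period; an intervention effect of -0.8 on the log-odds of craving; a person-level random intercept with SD 1.5; a waist slope of 4 cm per unit change in proportion; a direct effect of -1 cm; a residual SD of 5 cm; no true interaction; 400 replicates. Results are averages over replicates.

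- One mediator (change in proportion) in both paths: a = -0.140 and b = 3.98, so a × b = -0.556 cm.
- Cross-check, total minus direct effect: -1.550 - (-0.994) = -0.556 cm. The two agree.
- Using the mediator coefficient plus interaction from a Path C'-type model: a × (b + interaction) = -0.565 cm, close to the same value.
- Marginal log-odds for Path A times the Path B slope: -0.564 × 3.98 ≈ -2.24 cm, and 2.24 / 0.556 ≈ 4.0.
- Conditional log-odds for Path A times the Path B slope: -0.8 × 3.98 ≈ -3.18 cm, and 3.18 / 0.556 ≈ 5.7.

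With 8 reports per period the values are -0.551 cm for the common mediator, against -2.22 and -3.17 cm.

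**Step 4. What can still be estimated?** The planned Path C' model for waist regresses waist change on intervention and craving change, so it already holds an intervention-adjusted craving coefficient. The same texts supply the arm difference in craving change. For HOMA, Path B gives a usable coefficient if intervention is in that model. The text states this only for SSB consumption, and says the mediation model is run first without covariates.

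**The case against.** A reader might infer that no indirect effect can be formed for either primary outcome. The documents do not support that. Step 4 shows that the data and the planned Path C' model suffice for waist, and that HOMA needs only intervention terms in Path B. Nor do the outcomes differ throughout: SSB consumption, the outcome the plan itself designates, appears in B, C and C', and total-effect models exist for all outcomes.

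The plan also never says it will multiply the Path A and Path B coefficients. A joint test of the two paths needs no common scale, and the cited mediation sources and the path figure are not available here. This stands, so the 4- to 6-fold discrepancy shows what a literal product would do and is not evidence about this trial. The interaction term is not itself a defect; what is missing is the level at which the mediated effect is to be read.

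Finally, Aim 3 is labelled exploratory, and no primary comparison or sample size depends on it. That limits the consequence. It does not supply the missing definition, because a test of indirect effects on the primary outcomes is what the aim promises.

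**Conclusion.** The concern holds in limited form. As written, the Aim 3 plan does not consistently define the indirect effect for either primary outcome. The mediator changes unit, scale and window between Path A and Paths B and C', and neither HOMA nor waist is named in both B and C'. The Path A and Path B coefficients cannot be multiplied directly; on the assumed inputs, doing so overstates the indirect effect about 4 to 6 times. This rests on reading the outcome lists literally, and on Path C' using the craving change defined in Path B. If the lists are shorthand for all outcomes, the mediator mismatch and the missing estimator remain. The gap is one of specification, not of data, and the Aim 1 and 2 analyses are unaffected. It should be corrected before the Aim 3 analysis is run.

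**What to change.** Amend the Analytic Plan for Aim 3 as follows.

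1. **One mediator in every path:** each person's change, from baseline to 6 months, in the proportion of evening reports with a craving.
2. **One mediator model:** this change regressed on ban, counselling and their interaction.
3. **One outcome model,** fitted alike to 12-month SSB intake, HOMA and waist: intervention terms, craving change, and intervention by craving change, with the same covariates and one outcome form throughout.
4. **A stated estimand:** for a named contrast (for example both interventions against neither), the modelled difference in craving change times the craving slope, including interaction terms, at a stated intervention level.
5. **Intervals that account for campus,** with a note that only 16 campuses limit a cluster bootstrap.
6. **Craving acted upon** handled the same way as a separate second mediator, so that it is not lost.
7. **The daily logistic model** kept as descriptive.

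Cost: plan wording and modest extra programming. No new data are needed: waist, bloods and beverage intake are scheduled at baseline and 12 months, and craving texts at baseline and 6 months. The downside is that the daily-level model no longer supplies Path A, and each person's proportion rests on about four reports per period.

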Analytic Plan for Aim 2: Having established the main effects of each intervention under Aim 1, our analyses for Aim 2 focus on the interaction between them. Specifically, we anticipate that the combined intervention will have an effect above and beyond the simple additive effects of the two interventions. This analysis will require replicating the ANOVA and regression models used for Aim 1 with the addition to each of an interaction term for the two interventions. For example, the model predicting HOMA change will include assignment to the sales ban condition (coded as 0/1), assignment to the brief intervention condition (coded as 0/1), the interaction term for the two conditions (sales ban*brief intervention), baseline HOMA, baseline SSB consumption, baseline BMI, race/ethnicity, job classification (if sample size allows, as above), and sex. The procedure for analyzing each outcome is the same, but with each primary and secondary outcome substituted for HOMA in turn. This time, the main variable of interest will be the interaction term. We will graph and deconstruct each significant interaction term to determine the details of the interaction.

Power Calculations: As with Aim 1 above, power calculations are based on findings from the UCSF pilot and retention rates from the Sutter pilot. We will have 175 participants in each of the following groups. With 80% retention, this allows a final N of 550, with approximately 138 in each of the four experimental conditions. Power analysis for a full factorial design conducted with the BDEsize¹⁰⁹ package within R¹¹⁰ indicates that at 80% power and an alpha level of .05 we will be able to detect effect sizes as small as .12 for the interaction between the two interventions.

Anticipated Problems and Alternative Approaches: As with Aim 1, attrition and self-report bias are the primary potential issues we anticipate; handling of each is described above.

Expected Outcomes: We anticipate a significant interaction term, and more specifically, that the effect of the sales ban and brief intervention together will be stronger than each is individually. Participants assigned to the brief intervention and working at sites with a sales ban would thus demonstrate the greatest amount of change, and more change than one would expect if the effect of the two conditions were simply additive.

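### Aim 3's Path C' intervention coefficient is the effect at zero craving change, so reading it as the direct effect, or against Path C, can misstate mediation

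*Combined protocol and SAP*

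**What the plan says.** All of this is in section (4c), Methods of Data Analysis, of the combined protocol and SAP.

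- **Path C.** The Analytic Plan for Aim 3 states: "The relationship between the interventions and SSB consumption without the inclusion of craving (Path C) will have already been established", and refers to the Aim 1 and Aim 2 analyses. Those models contain 0/1 indicators for the sales ban and for counselling, baseline covariates and, in Aim 2, the ban-by-counselling product. They contain no craving term.
- **Path C'.** This is described as "interventions predicting consumption and waist change with the inclusion of the craving mediator". The model is like those of Aims 1 and 2, but "with the addition of craving change and an interaction term for intervention*craving change".
- **The mediator.** For Path B, craving change runs from baseline to the 6-month follow-up and is "measured as the change in the proportion of responses in which subjects reported cravings". Zero therefore means no change. No centring is stated there or for Path C'.
- **Indirect effects.** The Research Design for Aim 3 says the analysis will "simultaneously test all paths, including indirect effects through the mediator". It gives no formula and does not say how direct and indirect effects are defined once the product term is in the model.
- **Data used.** The Aim 1 Analytic Plan uses all data collected at the three time points. Aim 3 does not say whether Path C will be refitted in those who have craving data.

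**The concern.** Path C is the total effect. Path C' is the intervention effect with the mediator in the model, and setting one beside the other is the usual way to see how much of an effect passes through a mediator. With a product term present, the intervention coefficient no longer has one value. It is the effect at whatever craving change is coded zero, and here that is no change in craving. If craving falls on average in the comparison group, zero is not a typical value even there, and the coefficient is not the direct effect at the craving change that occurs.

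At stake is what Aim 3 says about craving as an active ingredient. A shift from C to C' could look large with modest mediation, or look absent when there is some. A second source of shift is the sample: if C' is fitted only in people with craving texts at both time points, part of any difference from C reflects who is included.

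**Working it through.** Aim 3 states no sample size, power or mediated share, so there is no figure of the plan's to reproduce. The check is algebraic and uses one 0/1 intervention X, craving change M and outcome Y, without covariates.

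**Models**

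- Mediator: mean M = b0 + b1·X, where b0 is the reference group's mean craving change.
- Outcome: mean Y = t0 + t1·X + t2·M + t3·X·M.

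**What each quantity is**

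- Path C (total effect) = t1 + t2·b1 + t3·(b0 + b1)
- Path C' intervention coefficient = t1, the effect at M = 0
- C − C' = t2·b1 + t3·(b0 + b1)
- Total natural indirect effect = (t2 + t3)·b1
- Pure natural indirect effect = t2·b1

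C − C' therefore exceeds the total indirect effect by t3·b0, and the pure indirect effect by t3·(b0 + b1).

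**Illustration.** All values are assumed; none is from the documents. Total effect −12 oz/day, b1 = −0.20, t2 = 20 oz/day per unit of craving proportion. The pure indirect share is 20 × (−0.20) / (−12) = 33% in every row.

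| t3 | Total indirect share | (C − C')/C at b0 = 0 | b0 = −0.05 | b0 = −0.10 | b0 = −0.20 |
|---|---|---|---|---|---|
| 0 | 33% | 33% | 33% | 33% | 33% |
| 10 | 50% | 50% | 54% | 58% | 67% |
| 20 | 67% | 67% | 75% | 83% | 100% |
| −10 | 17% | 17% | 12.5% | 8% | 0% |

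One cell in full (t3 = 10, b0 = −0.10): C − C' = 20 × (−0.20) + 10 × (−0.30) = −7, and 7/12 = 58%. The total indirect effect is 30 × (−0.20) = −6, and 6/12 = 50%. The gap is 10 × (−0.10) = −1 oz/day. Least squares on 400,000 simulated participants per scenario matched every C − C' share to within 0.01.

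**The sign can also reverse.** Take t1 = −2, t2 = 8, b0 = −0.20, b1 = −0.15, again assumed.

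- t3 = 8: C = −2 − 1.2 − 2.8 = −6.0 and C' = −2.0, an apparent share of 4.0/6.0 = 67%. The total indirect effect is 16 × (−0.15) = −2.4 (40%); the pure one is −1.2 (20%).
- t3 = −8: C = −2 − 1.2 + 2.8 = −0.4 and C' = −2.0, so C' is five times C. The total indirect effect is 0; the pure one is still −1.2.

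**Effect of centring.** With M centred at the reference-group mean, the intervention coefficient becomes t1 + t3·b0, and C minus it is (t2 + t3)·b1, the total indirect effect. In the simulations for the table this recovered about 50%, 67% and 17% for t3 = 10, 20 and −10.

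**Is a non-zero b0 likely?** Path C' is modelled on Aims 1 and 2. In the Aim 1 form, without a ban-by-counselling term, the comparison group for counselling includes employees at ban campuses, where fewer cues are meant to reduce craving. A mean change of exactly zero is not what the investigators expect there.

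**The case against.** A reader might infer that the plan will subtract C' from C and report a mediated share. The documents do not say so. They promise a simultaneous test of all paths, including indirect effects, and the craving quantity that they name is a proportion of variance in consumption. For Aim 2 the plan undertakes to plot and take apart significant interactions, which suggests that the team would not read main coefficients alone. Including the product term is also legitimate in itself.

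A reader might also take the pilot as evidence that the interaction is non-zero. The pilot result (−19.21 against −2.49 oz/day among those with strong cravings) concerns baseline craving, not change in craving after randomisation. It shows nothing direct about t3. Nor is there one true mediated share when t3 is not zero: total and pure indirect effects differ.

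Finally, a difference in participants is an inference. Craving texts may be incomplete, since the gift code needs only 6 of 8, but a common sample is neither stated nor excluded.

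These points make the concern conditional; they do not remove it. Pairing a path without craving with one that includes it has little purpose other than comparing total with direct effect. The Aim 2 undertaking does not cover the Aim 3 product term. No rule for direct or indirect effects under the interaction appears anywhere. Even with no subtraction, C' read alone as the direct effect is still the effect at zero craving change.

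**Conclusion.** The point holds in conditional form. As specified, the Path C' intervention coefficient is the model-based effect at zero craving change. It is not an estimate from the subgroup whose craving did not change. Reading it as the direct effect, or against Path C, can misstate mediation when both the interaction and the reference group's mean craving change are non-zero. If either is zero, C − C' equals the total natural indirect effect; it equals the pure one only if the interaction or the intervention group's mean change is zero.

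The documents do not fix the size. In the tabulated scenarios the error against the total indirect share runs from −17 to +33 percentage points. Those figures rest on assumed inputs, linear models, a single binary intervention and the choice of total rather than pure effect. A causal reading of any of these quantities also assumes no unmeasured common causes of craving change and outcome.

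The samples for C and C' are likely to differ, by an unknown amount. Only exploratory Aim 3 is affected, so this is a minor correction.

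**What to change.** In the Analytic Plan for Aim 3:

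1. Keep the product term and report the interaction as a separate test. Say which intervention it refers to, since the design has two interventions and their combination.
2. For each contrast (ban, counselling, combined), name the reference group and centre craving change at that group's mean. Alternatively, report natural or interventional direct and indirect effects from the fitted mediator and outcome models. State which indirect effect, total or pure, is meant.
3. Re-estimate Path C on the same participants, outcome and covariates as Path C'.

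The cost is modest extra analysis code and some plan wording, best settled before outcomes are analysed. The refitted Path C will lose those without craving data; the Aim 1 and Aim 2 estimates stay as they are. The second option in step 2 takes more work than centring, because Path A is on the log-odds scale while Path B uses change in a proportion. No new data are needed.
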